10.5.2.3 Overall Response Rate (ORR)

ORR is defined as the proportion of patients with best overall response of complete response (CR) or partial response (PR) based on local investigator's assessment according to RECIST 1.1. It will be calculated along with the exact binomial two-sided 95% confidence interval ([Clopper 1934](#)) by treatment arm for the *PIK3CA* mutant and non-mutant cohorts. In addition, ORR analyses based on blinded independent central review will be performed, if relevant.

10.5.2.4 Clinical benefit rate

Clinical benefit rate is defined as the proportion of patients with a best overall response of CR or PR or SD or Non-CR/Non-PD lasting more than 24 weeks based on local investigator assessment. It will be calculated along with the exact binomial two-sided 95% confidence interval ([Clopper 1934](#)) by treatment arm for the *PIK3CA* mutant and non-mutant cohorts. In addition, clinical benefit rate analyses based on blinded independent central review will be performed, if relevant.

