10.5.2 Other secondary efficacy objectives

Analyses will be based on the FAS.

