If the true hazard ratio is 0.6 (under alternative hypothesis), a total of 243 PFS events are required to have 83.80% power at an one-sided overall 2.0% level of significance to reject the null hypothesis (HR.=1) using a log-rank test for a 3-look group sequential design using a Haybittle-Peto boundary to determine the efficacy boundary along with (i) a gamma spending function ($\gamma = 5$) and (ii) a conditional probability function to determine the non-binding futility boundaries. Assuming that 40% of the patients will have a *PIK3CA* mutant status, an enrollment rate of 12 patients during the first 6 months (5 with *PIK3CA* mutant status), 35 patients up to 12 months (14 with *PIK3CA* mutant status) and 59 patients afterwards (24 with *PIK3CA* mutant status) and 10% patients will be lost to follow-up for PFS final analysis, a total of 340 patients will need to be randomized in this cohort to the two treatment arms in a 1:1 ratio. Given the above assumptions, it is estimated that the 243rd PFS event will be observed at approximately 32 months from the date of first patient randomized in the cohort.

The estimated timelines for interim and final PFS analyses are provided in [Table 10-4](#).

Table 10-4 Estimated timelines for interim and final PFS analyses in the *PIK3CA* mutant cohort

Look	Months after randomization of the first patient	Number of PFS events	Number of patients expected to be randomized (HR.=1).
Interim 1 (futility)	19	97	271
Interim 2 (efficacy)	25	185	340
Final	32	243	340

Patients with *PIK3CA* non-mutant status:

The proof of concept criteria require:

(a) an estimate for PFS HR reaching a critical value i.e. $HR \leq 0.60$

(b) strong evidence that the treatment results in a HR that is better than the value of no interest. i.e. Posterior Probability (HR < 1) $\geq 90\%$

Based on the dual criteria a minimum of 102 PFS events are required (please refer to [Section 14.6](#)). Assuming an enrollment rate of 12 patients during the first 6 months (7 with *PIK3CA* non-mutant status), 35 patients up to 12 months (21 with *PIK3CA* non-mutant status) and 59 patients afterwards (35 with *PIK3CA* non-mutant status) and 10% patients will be lost to follow-up, 220 patients will be randomized (110 per arm), in order to observe the required 102 PFS events in approximately 18 months (if the observed HR is 0.60 and the median PFS for the control arm is 7.4 months).

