2.2 Data included in the analysis

A unique cut-off date will be established after the targeted number of events for each of the planned interim and final efficacy analyses has been documented.

For the primary analysis CSR, all efficacy analyses will be based on separate cut-off dates determined for each of the PIK3CA mutant and non-mutant cohorts, based on the target number of PFS events specified in [Section 3.12](#) (i.e. final PFS analyses data cut-off date for PIK3CA non-mutant cohort; interim efficacy or final PFS analyses data cut-off date for PIK3CA mutant cohort). For the primary analysis CSR, all safety analyses for both PIK3CA cohorts will be based on the data cut-off date for the interim efficacy or final PFS analysis in the PIK3CA mutant cohort.

For each of the analyses, all statistical analyses will be performed using all data collected in the database up to the data cut-off date. All data with an assessment date or event start date (e.g. vital sign assessment date or start date of an adverse event) prior to or on the cut-off date will be included in the analysis. Any data collected beyond the cut-off date will not be included in the analysis and will not be used for any derivations.

All events with start date before or on the cut-off date and end date after the cut-off date will be reported as ‘continuing at the cut-off date’. The same rule will be applied to events starting before or on the cut-off date and not having documented end date. This approach applies, in particular, to adverse event and concomitant medication reports. For these events, the end date will not be imputed and therefore will not appear in the listings.

Interim review of safety data will be provided in each cohort as well as pooled across both cohorts, at each DMC meeting where safety data is reviewed. It is planned that the first DMC safety review meeting will be based on at least 2 months’ exposure data from approximately the first fifty patients, or available data after at least 6 months after the first patient is randomized, whichever date occurs first. Subsequent formal safety reviews will be based on data available every six months (+/-30 days window) after the first meeting, unless otherwise requested by the DMC.

Withdrawal of Informed Consent

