3.8.2 Secondary efficacy analyses

The analysis of all secondary efficacy endpoints will be performed, where appropriate, based on the FAS for i) cohort of patients with PIK3CA mutant status, and ii) cohort of patients with PIK3CA non-mutant status.

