3.8.2.6 Clinical benefit rate

Clinical benefit rate is defined as the proportion of patients with a best overall response of CR or PR or SD or Non-CR/Non-PD lasting 24 weeks or more based on local investigator assessment according to RECIST 1.1 criteria.

A patient will be considered to have SD for 24 weeks or longer if a SD response is recorded at 24-1=23 weeks or later from randomization, allowing for the ± 1 week visit window for tumor assessments. Patients with only non-measurable disease at baseline will be part of the analysis and will be included in the numerator only if they achieve a complete response or have a 'Non-CR/Non-PD' response 23 weeks or more after randomization.

CBR will be presented along with the exact binomial two-sided 95% confidence interval (Clopper 1934) by treatment arm for the *PIK3CA* mutant and non-mutant cohorts.

In addition, CBR in the subset of patient with measurable disease at baseline will be presented.

As a supportive analysis, CBR will also be summarized based on the central radiology review of tumor data, if the BICR moves to a 100% audit.

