If the true hazard ratio is 0.6 (under alternative hypothesis), a total of 243 PFS events are required to have 83.80% power at an one-sided overall 2.0% level of significance to reject the null hypothesis (HR.=1) using a log-rank test for a 3-look group sequential design using a Haybittle-Peto boundary to determine the efficacy boundary along with (i) a gamma spending function ($\gamma = 5$) and (ii) a conditional probability function to determine the non-binding futility boundaries. Assuming that 40% of the patients will have a *PIK3CA* mutant status, an enrollment rate of 12 patients per month during the first 6 months (5 per month with *PIK3CA* mutant status), 35 patients per month up to 12 months (14 per month with *PIK3CA* mutant status) and 59 patients per month afterwards (24 per month with *PIK3CA* mutant status) and 10% patients will be lost to follow-up for PFS final analysis, a total of 340 patients will need to be randomized in this cohort to the two treatment arms in a 1:1 ratio. Given the above assumptions, it is estimated that the 243rd PFS event will be observed at approximately 32 months from the date of first patient randomized in the cohort.

The estimated timelines for interim and final PFS analyses are provided in [Table 3-13](#).

Table 3-13 Estimated timelines for interim and final PFS analyses in the *PIK3CA* mutant cohort

Look	Months after randomization of the first patient	Number of PFS events	Number of patients expected to be randomized (HR.=1).
------	---	----------------------	---

Interim 1 (futility)	19	97	271
Interim 2 (efficacy)	25	185	340
Final	32	243	340

Patients with PIK3CA non-mutant status:

The proof of concept criteria require:

- (a) an estimate for PFS HR reaching a critical value i.e. $HR \leq 0.60$
- (b) strong evidence that the treatment results in a HR that is better than the value of no interest. i.e. Posterior Probability ($HR < 1$) $\geq 90\%$

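### At the non-mutant PFS cut-off, and at the mutant efficacy interim if that becomes the cut-off, about 12% of the FAS cannot yet qualify for CBR through stable disease, so CBR is biased low

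*Protocol*

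**What the plan says.** - **Definition.** Protocol 10.5.2.4 gives CBR as the "proportion of patients with a best overall response of CR or PR or SD or Non-CR/Non-PD lasting more than 24 weeks". SAP 3.8.2.6 sets the duration at 24 weeks or more, and treats a patient as stable for that long "if a SD response is recorded at 24-1=23 weeks or later from randomization". Non-CR/Non-PD in patients without measurable disease follows the same week-23 rule.
- **Denominator.** Protocol 10.5.2 states: "Analyses will be based on the FAS". SAP 3.8.2 agrees: "The analysis of all secondary efficacy endpoints will be performed, where appropriate, based on the FAS". The FAS is every randomised patient in the cohort.
- **Cut-off.** For the primary study report, SAP 2.2 ties efficacy to PFS events: "final PFS analyses data cut-off date for PIK3CA non-mutant cohort; interim efficacy or final PFS analyses data cut-off date for PIK3CA mutant cohort".
- **Timing.** Protocol 10.8 randomises 220 non-mutant patients "in order to observe the required 102 PFS events in approximately 18 months". The mutant cohort has 340 patients, with its efficacy interim planned at month 25 and final PFS at month 32.
- **Reporting.** CBR is given by arm and cohort with an exact 95% confidence interval. No hypothesis test is attached.

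Neither CBR section sets a minimum follow-up, or a rule for a patient whose stable disease is ongoing but shorter than 23 weeks at the cut-off.

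**The concern.** Stable disease counts as benefit only once it has lasted about 24 weeks. A patient randomised less than that before the cut-off cannot meet the condition, however well the disease is controlled. Such a patient stays in the denominator and is scored as no benefit, because of the randomisation date and not because of the disease. Protocol 10.7.1 holds the mutant efficacy interim until all mutant patients are randomised, but that does not give the last of them 24 weeks of follow-up.

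CBR is a listed secondary endpoint for both cohorts. At stake are its estimate and interval in the primary study report, the size of any arm difference that comes from stable disease, and comparability between cohorts. If mutant CBR is reported at month 32 and non-mutant CBR at month 18, only the non-mutant figure is truncated.

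**Working it through.** **Inputs.** Monthly accrual (SAP 3.14): mutant 5, then 14, then 24; non-mutant 7, then 21, then 35, with the rate changing at months 6 and 12. Cohort sizes: 340 and 220. Control median PFS 7.0 and 7.4 months, hazard ratio 0.6, 10% lost to follow-up. One month is 30.4375 days (SAP 2.1.12), so 23 weeks = 161/30.4375 = 5.29 months and 24 weeks = 168/30.4375 = 5.52 months.

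**The plan's own figures.** The non-mutant event count is 4 × 2.576² / (ln 0.6)² = 101.7, which rounds up to the stated 102. Expected events were then integrated over the accrual, with exponential PFS and the 10% loss spread over 24 to 32 months:

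| Events | Computed month | Stated month |
|---|---|---|
| Non-mutant 102 | 17.8-17.9 | 18 |
| Mutant 185 | 25.0-25.1 | 25 |
| Mutant 243 | 31.9-32.2 | 32 |

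**Last patient in.**
- Non-mutant: 7×6 + 21×6 = 168 by month 12; the other 52 at 35 per month end at month 13.49. At month 18 the last patient has 4.5 months (19.6 weeks).
- Mutant: 5×6 + 14×6 = 114 by month 12; the other 226 at 24 per month end at month 21.42. At month 25 the last patient has 3.6 months (15.6 weeks); at month 32, 10.6 months.

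**Share with too little potential follow-up.** Share = [N − number randomised by (cut-off − threshold)] / N.

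| Cut-off | Threshold | Randomised in time | Too late | Share |
|---|---|---|---|---|
| Non-mutant, month 18 | 23 weeks | 168 + 0.71×35 = 192.9 | 27.1 of 220 | 12.3% |
| Non-mutant, month 18 | 24 weeks | 168 + 0.48×35 = 184.8 | 35.2 of 220 | 16.0% |
| Mutant, month 25 | 23 weeks | 114 + 7.71×24 = 299.1 | 40.9 of 340 | 12.0% |
| Mutant, month 25 | 24 weeks | 114 + 7.48×24 = 293.5 | 46.5 of 340 | 13.7% |
| Mutant, month 32 | either | 340 | 0 | 0% |

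Unrounded accrual rates (4.8/14/23.6 and 7.2/21/35.4) give 13.3-14.9% for the mutant interim and 11.7-15.4% for the non-mutant cohort. If alpelisib has no effect there, Protocol Table 10-5 expects the non-mutant analysis at month 16.0, and the share is then 36-38%.

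**Points lost.** Loss = share too late × proportion who would qualify through lasting stable disease. The documents give no such proportion for fulvestrant 500 mg.
- At 25%: 0.12×25 = 3.0 to 0.16×25 = 4.0 points. This proportion is close to 32.2 − 7.4 = 24.8, from the fulvestrant 250 mg arm of a phase III trial in Protocol 1.2.1.
- At 35% (for example CBR 60% and response 25%, both assumed): 0.12×35 = 4.2 to 0.16×35 = 5.6 points.

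These are illustrations, not bounds. Under the plan's exponential PFS, 60.9% of non-mutant control patients are progression-free at 23 weeks. If none qualified earlier through CR or PR, the loss would be 12.3% × 60.9% = 7.5 points (9.2 points in the alpelisib arm). Across both cohorts, arms and thresholds this ceiling runs from 7.1 to 11.7 points. It falls to about 4-10 points if 10-25% qualify through CR or PR (assumed).

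**Arm difference.** The stable-disease part shrinks by the same share: an illustrative 10-point difference loses 1.2-1.6 points.

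**The case against.** The other side has good points.

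- **Scope.** A reader might infer that CBR is truncated at every event-driven cut-off. It is not. The mutant final PFS analysis is free of it, and the efficacy interim becomes the mutant cut-off only if p ≤ 0.0001, which Protocol Table 10-1 puts at 38.50% under a hazard ratio of 0.6. This stands.
- **Consequence.** No alpha and no decision rule depends on CBR, and both arms follow the same calendar rule. With 110 per arm and CBR near 32%, the 95% half-width for a difference is about 12 points, far more than the 1.2-1.6 points above. This stands.
- **Later data.** Protocol 4.3 has all data up to the final cut-off analysed. That is true, but it does not name CBR, and SAP 2.2 fixes the earlier cut-offs for the primary report.
- **A censoring-adjusted counterpart.** SAP 3.8.1.3 reports Kaplan-Meier PFS at 6 months. It belongs to the primary endpoint; for non-mutant PFS, SAP 3.8.2.2 lists only medians. It does not correct CBR.
- **Intention to treat.** Keeping every randomised patient in the denominator follows the plan's stated principle. Restricting to 25 weeks of potential follow-up would drop 43 of 220 and 52 of 340 patients, some already classifiable. This is a fair reason to add the restricted figure and not to replace the FAS figure.

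**Conclusion.** The point holds in limited form. At the non-mutant final PFS cut-off, and at the mutant cut-off only if PFS is declared at the efficacy interim, about 12% of the FAS under the SAP's week-23 rule (14-16% under a 24-week rule) cannot yet qualify for CBR through SD or Non-CR/Non-PD. CBR is therefore biased low in both arms, and an arm difference that comes from stable disease is reduced, not reversed.

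Two stronger readings are not supported. The 12-16% is not itself the bias, because only patients who would have qualified through lasting stable disease are lost. Nor do the documents establish how many points are lost: about 3-4 and 4-6 follow from assumed proportions of 25% and 35%.

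All shares rest on planned accrual and timing. The documents date the end of enrolment (29 September 2016 non-mutant, 21 July 2017 overall) but not the cut-offs, so the realised share cannot be computed. This is a reporting defect worth correcting; it does not affect the trial's formal tests.

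**What to change.** In Protocol 10.5.2.4 and SAP 3.8.2.6, keep the full-FAS CBR and do one of the following:

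1. Add a pre-specified CBR by arm, with exact interval, in FAS patients randomised at least 25 weeks before the cohort's cut-off (24 weeks plus the 1-week scan window). Since 25 weeks = 175/30.4375 = 5.75 months, this keeps 168 + 0.25×35 ≈ 177 of 220 and 114 + 7.25×24 = 288 of 340 under planned accrual. Selection uses only the randomisation date, so the arms stay comparable.
2. Report non-mutant CBR at the later mutant cut-off, which SAP 2.2 already applies to non-mutant safety data. On planned timings, if both cohorts start together, that is at least 25 − 13.49 = 11.5 months after the last non-mutant randomisation, and no patient is dropped. It does not help the mutant interim, which still needs option 1.

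Also settle one duration rule: the protocol requires more than 24 weeks, the SAP 24 weeks or more, counted from week 23.

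Cost: one extra table. In the restricted set the interval is wider by about √(340/288) − 1 = 9% (mutant) to √(220/177) − 1 ≈ 12% (non-mutant).

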10.5.2.5 PFS in patients with *PIK3CA* mutant status measured in ctDNA

An analysis of PFS based on local radiology assessments and using RECIST 1.1 criteria for each of (i) patients with *PIK3CA* mutant status and (ii) patients with *PIK3CA* non-mutant status as measured in ctDNA at baseline will be conducted using the same analytical conventions as the primary analysis.

10.5.2.6 ECOG Performance Status

ECOG performance status will be used to assess physical health of patients. An analysis of the time to definitive deterioration of the ECOG performance status by one category of the score from baseline will be performed using Kaplan-Meier method. A deterioration is considered definitive if no improvements in the ECOG performance status is observed at a subsequent time of measurement during the treatment period following the time point where the deterioration is observed.

10.5.3 Safety objectives

10.5.3.1 Analysis set and grouping for the analyses

For primary safety analyses, the safety set will be used. All listings and tables will be presented by treatment arm for the *PIK3CA* mutant and non-mutant cohorts individually as well as combined.

The assessment of safety will be based mainly on the frequency of adverse events and on the number of laboratory values that fall outside of pre-determined ranges. Other safety data (e.g. ECG, vital signs) will be considered as appropriate. All safety data will be listed.

The overall observation period will be divided into three mutually exclusive segments:

1. pre-treatment period: from day of patient's informed consent to the day before first dose of study medication
2. on-treatment period: from day of first dose of study medication to 30 days after last dose of study medication
3. post-treatment period: starting at day 31 after last dose of study medication

10.5.3.2 Adverse events (AEs)

Summary tables for adverse events will include only adverse events that started or worsened during the on-treatment period, the ***treatment-emergent*** adverse events.

The incidence of treatment-emergent adverse events (new or worsening from baseline) will be summarized by system organ class and/or preferred term, severity (based on CTCAE v4.03 grades), type of adverse event, relation to study treatment by treatment arm. Deaths reportable as Serious Adverse Events and non-fatal serious adverse events will be listed by patient and tabulated by type of adverse event and treatment arm.

Serious adverse events, non-serious adverse events and adverse events of special interest (AESI) during the on-treatment period will be tabulated.

All deaths (on-treatment and post-treatment) will be summarized.

All AEs, deaths and serious adverse events (including those from the pre and post-treatment periods) will be listed and those collected during the pre-treatment and post-treatment period will be flagged.

10.5.3.3 Laboratory abnormalities

For laboratory tests covered by the CTCAE version 4.03, the study's biostatistical and reporting team will grade laboratory data accordingly. For laboratory tests covered by CTCAE, a Grade 0 will be assigned for all non-missing values not graded as 1 or higher. Grade 5 will not be used.

For laboratory tests where grades are not defined by CTCAE, results will be graded by the low/normal/high classifications based on laboratory normal ranges.

The following by-treatment summaries will be generated separately for hematology, biochemistry and urinary laboratory tests:

- Number and percentage of patients with worst post-baseline CTC grade (regardless of the baseline status)
- shift tables using CTCAE grades to compare baseline to the worst on-treatment value
- for laboratory tests where CTCAE grades are not defined, shift tables using the low/normal/high/(low and high) classification to compare baseline to the worst on-treatment value.
- listing of all laboratory data with values flagged to show the corresponding CTCAE grades and the classifications relative to the laboratory normal ranges.
- listing of all notable laboratory abnormalities (i.e., newly occurring CTCAE grade 3 or 4 laboratory toxicities)

In addition to the above mentioned tables and listings, [REDACTED], for example [REDACTED]

be specified in the statistical analysis plan.

Laboratory values collected later than 30 days after study treatment discontinuation will be flagged in the listings.

10.5.3.4 Other safety data

Summary statistics for data from other tests will be provided, notable values will be flagged, and any other information collected will be listed as appropriate.

Descriptive summary statistics will be provided for:

- ECGs: changes from baseline results
- Cardiac imaging: change from baseline to worst post-baseline in LVEF values
- Vital signs: number and percentage of patients with at least one post-baseline vital sign abnormality

Listings with flagged notable values and any other information collected will be provided as appropriate.

10.5.3.5 Supportive analyses for secondary objectives

Not applicable.

10.5.3.6 Tolerability

Tolerability will be studied in terms of dose reductions and drug interruptions due to AE. Reasons for dose reductions and interruptions will be listed and summarized by treatment.

10.5.4 Patient-reported outcomes

The EORTC QLQ-C30 questionnaire [REDACTED] will be used to collect patient's QoL data. [REDACTED]

[REDACTED] The global health status/QoL scale score of the QLQ-C30 is identified as the primary patient-reported outcome variable of interest. Physical functioning, emotional functioning and social functioning scale scores of the QLQ-C30, [REDACTED]

[REDACTED]

Scoring of PRO data and methods for handling of missing items or missing assessments will be performed according to the scoring manual and user guide for each respective patient questionnaire (Fayers et al 2001; Oemar and Janssen 2013; Cleeland et al 2009). No imputation procedures will be applied for missing items or missing assessments.

The number of patients completing each questionnaire and the number of missing or incomplete assessments will be summarized by treatment group for each scheduled assessment time points for each cohort. No formal statistical tests will be performed and hence no multiplicity adjustment will be applied. The FAS will be used for analyzing PRO data.

Descriptive statistics will be used to summarize QLQ-C30, [REDACTED], [REDACTED] at each scheduled assessment time point for each cohort. Additionally, change from baseline [REDACTED] will be summarized.

[REDACTED] Patients with an evaluable baseline score and at least one evaluable post baseline score during the treatment period will be included in the change from baseline analyses.

In addition, a repeated measurement analysis model may be used to compare the two treatment groups with respect to changes in the domain scores (global health status/QoL scale score, physical functioning, emotional functioning and social functioning scale scores of the QLQ-C30) [REDACTED] longitudinally over time.

Time to definitive 10% deterioration in the global health status/QoL, physical functioning, emotional functioning, and social functioning scales will be assessed in each cohort. The time to definitive 10% deterioration is defined as the time from the date of randomization to the date of event, which is defined as at least 10% relative to baseline worsening of the corresponding scale score or death due to any cause. If a patient has not had an event, time to deterioration will be censored at the date of the last adequate PRO evaluation. The distribution will be presented descriptively using Kaplan-Meier curves. Summary statistics from Kaplan-Meier distributions will be determined, including the median time to definitive 10% deterioration along with two-sided 95% confidence interval. Additionally, time to definitive deterioration with different cutoff definitions (e.g. 5%, 15%) may be specified in the statistical analysis plan as deemed appropriate. A stratified Cox regression will be used to estimate the hazard ratio, along with two-sided 95% confidence interval.

[REDACTED]

